## 8.4 Adverse Events, Serious Adverse Events, and Other Reportable Safety Events

The definitions of an AE or SAE, as well as the method of recording, evaluating, and assessing causality of AE and SAE and the procedures for completing and transmitting AE, SAE, and other reportable safety event reports can be found in Appendix 3.

Adverse events, SAEs, and other reportable safety events will be reported by the participant (or, when appropriate, by a caregiver, surrogate, or the participant's legally authorized representative).

The investigator and any designees are responsible for detecting, documenting, and reporting events that meet the definition of an AE or SAE as well as other reportable safety events. Investigators need to document if an SAE was associated with a medication error, misuse, or abuse.

The investigator, who is a qualified physician, will assess events that meet the definition of an AE or SAE as well as other reportable safety events with respect to seriousness, severity, and causality.

# 8.4.1 Time Period and Frequency for Collecting AE, SAE, and Other Reportable Safety Event Information

All AEs, SAEs, and other reportable safety events that occur after the participant's legally acceptable representative provides documented informed consent but before intervention randomization must be reported by the investigator if the event causes the participant to be excluded from the study, or is the result of a protocol-specified intervention.

From the time of intervention randomization through 42 days following cessation of study intervention, all AEs, SAEs, and other reportable safety events must be reported by the investigator.

Additionally, any SAE brought to the attention of an investigator at any time outside of the time period specified in the previous paragraph must be reported immediately to the Sponsor.

Investigators are not obligated to actively seek AEs or SAEs or other reportable safety events in former study participants. However, if the investigator learns of any SAE, including a death, at any time after a participant has been discharged from the study, the investigator must promptly notify the Sponsor.

All initial and follow-up AEs, SAEs, and other reportable safety events will be recorded and reported to the Sponsor or designee within the time frames as indicated in Table 3.

Table 3 Reporting Time Periods and Time Frames for Adverse Events and Other Reportable Safety Events

Type of Event	Reporting Time Period: Consent to Randomization/ Allocation	Reporting Time Period: Randomization/ Allocation through Protocol- specified Follow- up Period	Reporting Time Period: After the Protocol- specified Follow-up Period	Time Frame to Report Event and Follow-up Information to Sponsor:			
Nonserious Adverse Event (NSAE)	Report if: - due to protocol- specified intervention - causes exclusion	Report all	Not required	Per data entry guidelines			
Serious Adverse Event (SAE)	Report if: - due to protocol- specified intervention - causes exclusion	Report all	Report all	Within 24 hours of learning of event			
Pregnancy/ Lactation Exposure	Not applicable since participants are infants.						
Event of Clinical Interest (require regulatory reporting)	There are no events of clinical interest for this study.						
Event of Clinical Interest (do not require regulatory reporting)	There are no events of clinical interest for this study.						
Adverse Event of Special Interest (AESI)	Report if: - due to intervention - causes exclusion	Report all	Report Serious AESI in the same manner as SAE	Within 5 calendar days of learning of event (unless serious)			
Cancer	Report if: - due to intervention - causes exclusion	Report all	Report Serious Cancer in the same manner as SAE	Within 5 calendar days of learning of event (unless serious)			
Overdose	Not applicable	Report all	Not required	Within 5 calendar days of learning of event			

# 8.4.2 Method of Detecting AEs, SAEs, and Other Reportable Safety Events

Care will be taken not to introduce bias when detecting AEs and/or SAEs and other reportable safety events. Open-ended and nonleading verbal questioning of the participant is the preferred method to inquire about AE occurrence.

## 8.4.3 Follow-up of AE, SAE, and Other Reportable Safety Event Information

After the initial AE/SAE report, the investigator is required to proactively follow each participant at subsequent visits/contacts. All AEs, SAEs, and other reportable safety events, including pregnancy and exposure during breastfeeding, ECIs, cancer, and overdose will be followed until resolution, stabilization, until the event is otherwise explained, or the participant is lost to follow-up (as defined in Section 7.3). In addition, the investigator will make every attempt to follow all nonserious AEs that occur in randomized participants for outcome. Further information on follow-up procedures is given in Appendix 3.

## 8.4.4 Regulatory Reporting Requirements for SAE

Prompt notification (within 24 hours) by the investigator to the Sponsor of SAE is essential so that legal obligations and ethical responsibilities towards the safety of participants and the safety of a study intervention under clinical investigation are met.

The Sponsor has a legal responsibility to notify both the local regulatory authority and other regulatory agencies about the safety of a study intervention under clinical investigation. The Sponsor will comply with country-specific regulatory requirements and global laws and regulations relating to safety reporting to regulatory authorities, IRB/IECs, and investigators.

Investigator safety reports must be prepared for SUSARs according to local regulatory requirements and Sponsor policy and forwarded to investigators as necessary.

An investigator who receives an investigator safety report describing an SAE or other specific safety information (eg, summary or listing of SAE) from the Sponsor will file it along with the IB and will notify the IRB/IEC, if appropriate according to local requirements.

## 8.4.5 Pregnancy and Exposure During Breastfeeding

Information in this section is not applicable, as participants are infants.

# 8.4.6 Disease-related Events and/or Disease-related Outcomes Not Qualifying as AEs or SAEs

Not applicable for this study.

#### **8.4.7** Events of Clinical Interest

Not applicable; there are no ECIs defined for this study.

# 8.4.8 Adverse Events of Special Interest

All AESI occurring through Day 42 postdose will be reported to the Sponsor. After Day 42, only AESI that meet the serious AE criteria (see Section 10.3.3) should be reported to the Sponsor.

The investigator will provide an assessment of severity for AESI according to the grading scales provided in both Section 10.3.5 and the Severity Grading for Adverse Events document, which are based on an adaption of the NCI CTCAE, version 5.

# 8.4.8.1 Anaphylaxis/Hypersensitivity Events

The following anaphylaxis/hypersensitivity events (Table 4) are defined as AESI in this study. The Sponsor will provide each site with an AESI guidance document (or equivalent). Refer to the AESI guidance document for the most updated list of terms, definitions, and additional details.

Table 4 Terms for Anaphylaxis/Hypersensitivity Events

Term	Definition
Anaphylaxis	A disorder characterized by an acute inflammatory reaction resulting from the release of histamine and histamine-like substances from mast cells, causing a hypersensitivity immune response.
	Clinically, it presents with breathing difficulty, dizziness, hypotension, cyanosis, and loss of consciousness and may lead to death.
Angioedema	Localized, non-pitting, and transient swelling of submucosal or subcutaneous region.
Bronchospasm	A disorder characterized by a sudden contraction of the smooth muscles of the bronchial wall.
Drug hypersensitivity (drug-related allergic reaction)	Adverse effects of drugs that clinically resemble allergic reactions. Immediate clinical manifestations may include urticaria, angioedema, rhinitis, conjunctivitis bronchospasm, and anaphylaxis. Delayed clinical manifestations may include urticaria, maculopapular eruptions, fixed drug eruptions, vasculitis, toxic epidermal necrolysis (TEN), Stevens-Johnson syndrome (SJS), drug reaction with eosinophilia and systemic symptoms (DRESS), and acute generalized exanthematous pustulosis (AGEP).
Dyspnea (difficulty breathing)	A disorder characterized by an uncomfortable sensation of difficulty breathing.
Hypersensitivity	Excessive immune response.  Clinically, manifestations may include allergic manifestations such as urticaria, anaphylaxis, angioedema, allergic rhinitis, Stevens-Johnson syndrome (SJS), toxic epidermal necrolysis (TEN), acute generalized exanthematous pustulosis (AGEP), drug reaction with eosinophilia and systemic symptoms (DRESS), serum sickness, and vasculitis.

Confidential

Term	Definition
Dysphonia	A disorder characterized by an inflammation involving the larynx.
Wheezing	A disorder characterized by a high-pitched, whistling sound during breathing. It results from the narrowing or obstruction of the respiratory airways.

Before study start, the investigator or medically qualified designee will receive support from the Sponsor to assist in identifying the anaphylaxis/hypersensitivity AESI terms listed above in addition to instructions on the process from identification to data entry. At Visit 1, the investigator will provide anticipatory guidance to the legally acceptable representative for a suspected anaphylaxis or hypersensitivity event.

If any anaphylaxis/hypersensitivity event is reported in the eDiary (through Day 42) or during weekly surveillance calls, further assessment by the site may be required. The site must call the legally acceptable representative for additional information; if it is determined that an onsite assessment is required, a site visit should be conducted as soon as possible after becoming aware of the anaphylaxis/hypersensitivity event or within 3 days.

In addition, the legally acceptable representative should call the site as soon as possible if they suspect an anaphylaxis/hypersensitivity event or within 3 days of event onset.

In the event a participant experiences a Grade 3 or 4 anaphylaxis/hypersensitivity AESI postdose, as confirmed by the investigator, an additional blood draw is required for evaluation for potential ADA to MK-1654, and additional ADA characterization, if indicated (see Section 1.3.1 and Appendix 2).

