### 3 HYPOTHESES, OBJECTIVES, AND ENDPOINTS

Hypotheses are aligned with objectives in the Objectives and Endpoints table.

The following objectives will be evaluated in healthy pre-term and full-term infants receiving a single IM dose of MK-1654 or placebo.

Objectives	Endpoints				
Primary					

 
To evaluate the efficacy of MK-1654 compared to placebo as assessed by the incidence of RSV-associated MALRI (outpatient and inpatient) from Days 1 through 150 postdose.
 
Hypothesis: Administration of MK-1654 reduces the incidence of RSV-associated MALRI from Days 1 through 150 postdose compared to placebo (The statistical criterion for success requires the lower limit of the 95% CI for efficacy to be greater than 25%).
 
	
 
RSV-associated MALRI (outpatient and inpatient), defined as the following seen in an outpatient or inpatient clinical setting:
 
Cough or difficulty breathing; AND
 
1 or more of the following: wheezing, chest wall indrawing/retractions, rales/crackles, hypoxemia, tachypnea, dehydration due to respiratory symptoms; AND
 
RSV-positive RT-PCR NP sample
 
				
To evaluate the safety and tolerability of MK-1654 compared to placebo as assessed by the proportion of participants experiencing AEs.	
 
Solicited injection-site AEs from Days 1 through 5 postdose
 
Solicited daily body temperature, with fever defined as rectal temperature ≥102.2°F (≥39.0°C) or axillary temperature ≥101.7°F (≥38.7°C), from Days 1 through 5 postdose
 
Solicited systemic AEs from Days 1 through 5 postdose
 
Anaphylaxis/hypersensitivity AESI from Days 1 through 42 postdose
 
Rash AESI from Days 1 through 42 postdose
 
Nonserious AEs from Days 1 through 42 postdose
 
SAEs through the duration of study participation
 
				

Confidential

Objectives	Endpoints
Secondary	

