## 9.4.1 Efficacy/Pharmacokinetics/Pharmacodynamics/Immunogenicity Endpoints

# **Efficacy Endpoints**

The primary efficacy endpoint that will be used to evaluate and test the primary efficacy hypothesis is the number of participants with RSV-associated outpatient and inpatient MALRI occurring from Days 1 through 150 postdose, as described in Section 4.2.1.1. RSV-associated outpatient and inpatient MALRI is defined by the presence of the following seen in an outpatient or inpatient clinical setting: cough or difficulty breathing; AND 1 or more of the following: wheezing, chest wall in-drawing/retractions, rales/crackles, hypoxemia,

PROTOCOL/AMENDMENT NO.: 004-05

tachypnea, dehydration due to respiratory symptoms; AND RSV-positive RT-PCR NP sample. The secondary efficacy endpoints are:

- Number of participants with RSV-associated hospitalization from Days 1 through 150 postdose, defined as hospital admission for respiratory illness; AND RSV-positive RT-PCR NP sample
- Number of participants with RSV-associated outpatient and inpatient MALRI from Days 1 through 180 postdose

The following are the tertiary efficacy endpoints for this study:

- Number of participants with RSV-associated outpatient and inpatient severe MALRI from Days 1 through 150 postdose
- Number of participants with RSV-associated outpatient and inpatient severe MALRI from Days 1 through 180 postdose
- Number of participants with RSV-associated hospitalization from Days 1 through 180 postdose
- Number of participants with outpatient and inpatient MALRI due to any cause from Days 1 through 150 postdose
- Number of participants with RSV-associated outpatient and inpatient MALRI from Days 365 through 515 postdose
- Number of participants with RSV-associated hospitalization from Days 365 through 515 postdose
- Number of participants hospitalized with RSV-associated LRI from Days 1 through 150 postdose
- Number of participants hospitalized with RSV-associated LRI from Days 1 through 180 postdose
- Number of participants hospitalized with LRI due to any cause from Days 1 through 150 postdose
- Number of participants with non-RSV-associated outpatient and inpatient MALRI from Days 1 through 150 postdose
- Number of participants with RSV-associated outpatient and inpatient MALRI excluding cases where other pathogens are found from Days 1 through 150 postdose
- Number of participants with RSV-associated outpatient and inpatient ARI from Days 1 through 150 postdose

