# 9.4.2 Safety Endpoints

Safety and tolerability of MK-1654 in this study will be assessed by clinical review of all relevant parameters including AEs and laboratory values. The endpoints that will be used to assess the safety and tolerability of MK-1654 include the following:

- Number of participants experiencing solicited injection-site AEs (redness/erythema, swelling, and pain/tenderness) from Days 1 through 5 postdose
- Number of participants experiencing solicited daily body temperature, with fever defined as rectal temperature ≥102.2°F (≥39.0°C) or axillary temperature ≥101.7°F (≥38.7°C), from Days 1 through 5 postdose
- Number of participants experiencing solicited systemic AEs (irritability, drowsiness, and appetite lost) from Days 1 through 5 postdose
- Number of participants with anaphylaxis/hypersensitivity AESI from Days 1 through 42 postdose

- Number of participants with rash AESI from Days 1 through 42 postdose
- Number of participants experiencing nonserious AEs occurring from Days 1 through 42 postdose
- Number of participants experiencing SAEs through the duration of study participation (from the time the consent form is signed through completion of the participant's participation in the study; for complete details on SAE data collection, see Section 10.3.5).

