### **Tier 3 Events**

Safety endpoints that are not Tier 1 or 2 events are considered Tier 3 events. Only point estimates by treatment group are provided for Tier 3 safety parameters.

Table 7 Analysis Strategy for Safety Parameters

Safety Tier	Safety Endpoint	95% CI for Comparison of MK-1654 and Placebo	Descriptive Statistics
Tier 2	Any AE a	X	X
	Any Serious AE	X	X
	Any Drug-related AE	X	X
	Any Serious and Drug-related AE	X	X
	Discontinuation due to AE	X	X
	Solicited Injection-site AEs Days 1-5 Postdose	X	X
	Solicited Daily Body Temperature Days 1-5 Postdose	Х	X
	Solicited Systemic AEs Days 1-5 Postdose	X	X
	Anaphylaxis/hypersensitivity AESI Days 1-42 Postdose	Х	X
	Rash AESI Days 1-42 Postdose	X	X
	Nonserious AEs Days 1-42 Postdose	X	X
	AEs by SOC (incidence ≥1% of participants in 1 of the treatment groups)	Х	X
Tier 3	AEs by SOC (incidence <1% of participants in all of the treatment groups)		X

AE=adverse event; AESI=adverse event(s) of special interest; SAE=serious adverse event; CI=confidence interval; SOC=System Organ Class; X=results will be provided.

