AESI Term	Grade 1	Grade 2	Grade 3	Grade 4	
Anaphylaxis	Not applicable	Not applicable	Symptomatic bronchospasm, with or without urticaria; parenteral intervention indicated; allergy-related edema/angioedema; hypotension	Life-threatening consequences; urgent intervention indicated	
Angioedema	Mild; asymptomatic or mild symptoms; clinical or diagnostic observations only; intervention not indicated; awareness of symptoms, but easily tolerated	Moderate; minimal, local or noninvasive intervention indicated. Infant is definitely acting like something is wrong	Severe or medically significant but not immediately life-threatening; intensive intervention indicated; disabling. Infant is extremely distressed or unable to do usual activities	Life-threatening consequences; urgent intervention indicated	
Bronchospasm	Mild symptoms; intervention not indicated	Symptomatic; medical intervention indicated; limiting routine activities such as feeding	Limiting routine activities such as feeding; supplemental oxygen indicated	Life-threatening respiratory or hemodynamic compromise; intubation or urgent intervention indicated	
Drug hypersensitivity (drug-related allergic reaction)	Allergic reaction; systemic intervention not indicated	Oral intervention indicated	Bronchospasm; hospitalization indicated for clinical sequelae; IV intervention indicated	Life-threatening consequences; urgent intervention indicated	
Hypersensitivity	Allergic reaction; systemic intervention not indicated	Oral intervention indicated	Bronchospasm; hospitalization indicated for clinical sequelae; IV intervention indicated	Life-threatening consequences; urgent intervention indicated	
Dyspnea (difficulty breathing)	Shortness of breath with moderate exertion	Shortness of breath with minimal exertion; limiting routine activities such as feeding	Shortness of breath at rest; limiting routine activities such as feeding	Life-threatening consequences; urgent intervention indicated	
Dysphonia	Mild sore throat; raspy voice	Moderate sore throat; analgesics indicated	Severe throat pain; endoscopic intervention indicated	Not applicable	
Wheezing  AESI-adverse eve	Detectable airway noise with minimal symptoms  ent(s) of special interest.	Moderate symptoms; medical intervention indicated; limiting routine activities such as feeding	Severe respiratory symptoms limiting routine activities such as feeding; oxygen therapy or hospitalization indicated	Life-threatening consequences; urgent intervention indicated	

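### The pooled hypersensitivity AESI counts wheezing, dyspnea and bronchospasm of any cause, so preventing RSV illness can lower it in the MK-1654 arm and dilute a true hypersensitivity excess

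*Combined protocol and SAP*

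**What the plan says.** Section 8.4.8.1 introduces the list with "The following anaphylaxis/hypersensitivity events (Table 4) are defined as AESI in this study". Wheezing, dyspnea (glossed as difficulty breathing) and bronchospasm stand there as terms of their own. Wheezing is defined as "A disorder characterized by a high-pitched, whistling sound during breathing", attributed to narrowed or obstructed airways. Neither the definition nor the table asks for a link to the drug or excludes infection. Table 16 grades wheezing as Grade 3 on "Severe respiratory symptoms limiting routine activities such as feeding; oxygen therapy or hospitalization indicated", a description that severe RSV illness can also meet.

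The primary efficacy endpoint (Section 9.4.1) requires "cough or difficulty breathing; AND 1 or more of the following: wheezing, chest wall in-drawing/retractions, rales/crackles, hypoxemia", among other signs, and a positive RSV PCR. Section 3 words the second limb as "1 or more of the following: wheezing, chest wall indrawing/retractions, rales/crackles, hypoxemia, tachypnea, dehydration due to respiratory symptoms".

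The AESI is a primary safety endpoint. Section 9.4.2 counts it as "Number of participants with anaphylaxis/hypersensitivity AESI from Days 1 through 42 postdose". Table 7 in Section 9.6.2 gives it one Tier 2 row, "Anaphylaxis/hypersensitivity AESI Days 1-42 Postdose", with a 95% CI for the arm difference by the Miettinen-Nurminen method (Section 9.1). Section 8.4.6, where disease-related events could be carved out of AE reporting, is marked not applicable.

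Section 10.3.5 limits the overlap: where the investigator establishes a diagnosis, that diagnosis is recorded in place of its signs.

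**The concern.** The AESI is there to detect a reaction to the antibody, which is expected to be uncommon. Two of its terms name signs that are common in RSV illness. Section 4.2.1.1 describes wheezes and crackles as the leading auscultatory findings, and the product is meant to prevent that illness. If RSV wheeze or dyspnea enters the AESI, it enters more often in the placebo arm. The arm difference then moves toward MK-1654 for a reason unrelated to hypersensitivity, and a small true excess becomes harder to see.

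No planned analysis separates the two sources. A specific allergic term below 1% in both arms falls to Tier 3, which gives point estimates only. The drug-related AE rows depend on investigator causality and are not specific to hypersensitivity. Elsewhere the plan does write a rule of the kind needed: Section 8.3.3 exempts fever from separate reporting when it belongs to another reported AE. Wheezing and dyspnea have no such rule in the text.

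**Working it through.** **Plan's own figures first.** Expected RSV-MALRI cases (Section 9.9.1.1): 1100 × 0.95 × 0.10 + 2200 × 0.95 × 0.03 = 104.5 + 62.7 = 167.2, against about 167 stated. Table 9 (2200 vs 1100, two-sided 5%, 80% power, pooled null variance) gives minimum detectable differences of 0.74, 1.76, 2.54, 3.35, 3.90, 4.31 and 4.85 points. All seven round to the printed values.

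**Inputs from the plan.** RSV-MALRI 10% (placebo) and 3% (MK-1654) per season; a 150-day efficacy window; a 42-day AESI window; 2200 and 1100 infants.

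**Assumptions.** RSV risk is even over the season. The non-RSV background is 0.1% or 2.0%, with true excesses of 0.7 and 1.8 points (the first two rows of Table 9). f, the share of RSV-MALRI cases in Days 1-42 recorded under a Table 4 term, is unknown and shown as a range.

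**Step 1: RSV-MALRI inside the AESI window.**
- All 42 days in season: placebo 10% × 42/150 = 2.80% (about 31 infants); MK-1654 3% × 42/150 = 0.84% (about 18). Gap 1.96 points.
- Dosed 4 weeks before onset, leaving 42 - 28 = 14 in-season days: 10% × 14/150 = 0.93% and 3% × 14/150 = 0.28%. Gap 0.65 points, one third of the above.

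**Step 2: shift in the AESI difference.** Observed difference = true excess - f × gap. The shift is -0.10, -0.20, -0.49 and -0.98 points at f = 5%, 10%, 25% and 50% with 42 in-season days, and -0.03, -0.07, -0.16 and -0.33 with 14.

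**Step 3: chance that the 95% CI lies above 0.** AESI risk is background + f × 0.84% + excess (MK-1654) and background + f × 2.80% (placebo), or with 0.28% and 0.93% for 14 days. The Miettinen-Nurminen score test at difference 0 was evaluated by simulation and confirmed by exact enumeration.

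| f | 0.7 points on 0.1%: 42 days | 14 days | 1.8 points on 2.0%: 42 days | 14 days |
|---|---|---|---|---|
| 0 | 84% | 84% | 82% | 82% |
| 5% | 58% | 75% | 76% | 80% |
| 10% | 36% | 66% | 70% | 78% |
| 25% | 7% | 42% | 49% | 72% |
| 50% | 0.4% | 17% | 20% | 60% |

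The 84% at f = 0 exceeds the 77% that the normal approximation behind Table 9 gives at the rounded 0.1% vs 0.8%. With so few events the approximation is rough, and the comparison down each column is what matters.

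**Step 4: full cancellation of a 0.7-point excess.** 0.7 / 1.96 = 36% with 42 in-season days. With 14 days, 0.7 / 0.65 exceeds 1, so it cannot occur through RSV-MALRI alone.

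**The case against.** The strongest reply is that f may be close to zero. RSV-MALRI cases are seen in a clinical setting, confirmed by the investigator and PCR-positive, so they are the cases most likely to be recorded as a diagnosis under Section 10.3.5. Section 8.4.8.1 also refers sites to an AESI guidance document, which is not among the documents reviewed and may deal with infectious wheeze. Part of the AESI window can fall before the season, since enrollment opens in the 4 weeks before onset. The plan calls Tier 2 intervals descriptive, gives further rows for drug-related events and rash AESI, and has the eDMC review interim safety data. Broad capture is defensible for a class with known hypersensitivity events.

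Much of this stands, and it rules out stronger readings:
- A reader might infer that preventing RSV necessarily lowers this AESI. The documents do not support that, because they do not give f and the diagnosis rule pushes it down.
- A reader might infer that a wheeze reported before its PCR result remains an AESI. Nothing says so: Section 8.4.3 follows events until they are explained, and Section 10.3.5 allows records to be updated.
- A reader might take the 73% labored breathing at the pediatrician's office cited in Section 4.2.1.1 as a value for f. It is the frequency of a sign among children with RSV, not the share recorded as an AESI.

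What the reply does not remove is the direction of the bias or its size at small f. The diagnosis rule applies only where a diagnosis is made, and it does not say that wheeze during a respiratory infection is not an AESI. Caregivers are instructed to look for AESI and enter them in the eDiary through Day 42, which favors capture. Enrollment continues until before the peak and in-season births are dosed soon after birth, so many windows lie in season. A rule for a primary safety comparison belongs in the analysis plan.

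**Conclusion.** The point holds in conditional form. To the extent that RSV illness is recorded as wheezing, dyspnea or bronchospasm, and MK-1654 works, the pooled AESI difference is biased toward MK-1654. The shift is -1.96 × f points with even risk and the whole window in season, and about one third of that with 14 in-season days. A small f is enough to matter for a rare event: at f = 5% to 10%, the chance of showing a 0.7-point excess drops from 84% to between 58% and 36%, or to between 75% and 66% in the 14-day case. The loss is milder on a 2.0% background.

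It would go too far to conclude that a true excess will be cancelled or reversed. That needs f above about 36% with in-season dosing.

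The result rests on the plan's 10% and 3%, even risk over 150 days, the assumed backgrounds and an unknown f. Dosing near the peak would raise the Days 1-42 share above 28%. Milder RSV wheeze would add to the shift. Wheeze from other viruses adds noise to both arms alike.

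**What to change.** Leave site reporting and the existing AESI row unchanged. In Section 9.4.2 and Table 7, pre-specify two supplementary rows with the same Miettinen-Nurminen 95% CI:

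- (a) the specific terms only: anaphylaxis, angioedema, drug hypersensitivity and hypersensitivity;
- (b) the full AESI, excluding wheezing, dyspnea and bronchospasm events whose onset lies within a respiratory episode that has an RSV-positive RT-PCR NP sample.

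Row (b) should require the positive PCR. Section 8.2.1.1 defines an episode by symptoms alone, so under a symptom-only exclusion a drug-induced wheeze could open an episode and remove itself. Dysphonia is not a MALRI criterion and should not be excluded. Show counts by term for each arm, and read the hypersensitivity conclusion from all rows together, not from row (b) alone.

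The cost is two table rows and a by-term listing. Episode dates and PCR results are already collected, and the change should be made before unblinding. The downside is that row (b) leaves out a true allergic wheeze that coincides with RSV infection, and row (a) leaves out isolated allergic wheeze. Both remain in the existing row.
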